6.3 Preliminary work

We have undertaken a retrospective cohort study and a UK-wide survey gathering data on the timing of PTP in patients following TBI. Our retrospective study included 731 patients over a six-month period and had participation from five neurosurgical centres. This study showed that 1) there was much heterogeneity in the timing of initiating PTP among different centres, 2) patients with major extracranial injuries were more likely to receive PTP and 3) PTP did not appear to exacerbate haemorrhagic intracranial lesions. Our UK-wide survey included responses from 61 individuals from 26 neuroscience units. The results showed 1) 85% of respondents agreed there is no high-quality evidence on the timing of starting PTP after an acute TBI and 2) the most common factors contributing to decision-making before starting VTE prophylaxis included progression of intracranial haemorrhage, new intracranial haemorrhage and prevention of VTE events. Thus, our preliminary work provides further evidence for the pressing need for standardised guidelines on this subject.

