9.1 Inclusion criteria

- Adult patients (≥ 16 years of age)
- Acute TBI (defined as acute traumatic changes on the CT brain, either in isolation or in the context of polytrauma)
- Patients admitted to hospital within 72 hours of injury

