9.2 Exclusion criteria

- Patients with recent VTE (within 3 months before TBI)
- Known hypersensitivity to any VTE prophylaxis agents used
- Patients are not expected to live beyond 72 hours
- The time interval from injury to randomisation exceeds 72 hours
- Participation in the same study within the last 12 months
- Current use of anticoagulation for an alternative indication, with a clinical decision to continue
- Active bleeding was deemed serious enough that the treating clinical team lacked equipoise for the study question
- Progression of early traumatic intracranial haemorrhage or unstable neurological condition, such that the treating clinical team lack equipoise for the study questions

Patients who fit the inclusion criteria and are on pre-existing anticoagulation (e.g. Warfarin for atrial fibrillation) should be managed as per standard hospital protocol. This would routinely involve stopping and reversing the agent. If there is a clinical indication to continue the anticoagulation for a reason other than for VTE prophylaxis, the patient will be excluded.

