9.3.2 Late PTP administration trial arm

Upon randomisation, patients will have PTP omitted. However, if deemed necessary by the clinical team, PTP prophylaxis can be administered 120 hours after injury. This will be continued until a clinical decision to stop. The VTE prophylaxis agent used route of administration and dose will be as per local hospital practice. The treating team will be encouraged to follow NICE guidance regarding the type and initiation of mechanical VTE prophylaxis.

We discussed the definition of late PTP at length with our multi-stakeholder group and patient representatives considering the feedback received at the stage 1 application. Our clinical stakeholders had significant reservations about being asked to defer PTP for >7 days in keeping with the currently running Canadian randomised trial (34). Our service evaluation data supports the proposal of deferring PTP in the late arm by a minimum of 5 days (120h), as the median time to PTP from TBI was 5 days in this population and in a recent prospective study in critically ill trauma patients the median time to VTE was 6 days (35). However, our advisory group highlighted the potential bias that may occur with mandated prophylaxis at 5 days, when our service evaluation suggests that 50% of this population currently receive no prophylaxis at all within routine care. As such, in the late arm, PTP will not be offered for the first 120 hours after injury; after 120 hours, PTP can be prescribed if deemed necessary by the clinical team. We believe these decisions are also supported by the existing literature as referenced above and offer the maximum opportunity for pragmatic recruitment, separation of

interventions and evaluation of the specific research question as to whether early initiation is better than managed consideration of risk in current practice.

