9.3.4. Randomisation

A secure web-based randomisation service (Sealed Envelope) will be used for the randomisation of eligible patients. Suitably trained staff will access the secure website and enter the necessary information. The system will provide an immediate allocation along with the patient identifier number for the trial. A confirmatory email will be sent to the email addresses of the study team members at the site randomising the patient. Trial investigators (or delegates) from the central team will be available 24-hours in case of problems or queries with the randomisation system. The presence of extracranial injury and initial admission to the ward vs critical care will stratify allocation. Stratified block randomisation will be used.

Early PTP arm - defined as administration of PTP within 72 hours of TBI

Late PTP arm - defined as administration of PTP after a minimum of 120 hours from TBI or PTP not administered at clinical discretion. PTP should not be administered within 120 hours and administration will be recorded as protocol deviation

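### The eligibility criteria do not address thromboprophylaxis given between injury and randomisation, so a patient can enter the late arm with its definition already broken

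*Protocol*

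**What the plan says.** **Eligibility (protocol 9.1 and 9.2).** The timing criterion for inclusion is "Patients admitted to hospital within 72 hours of injury", and an exclusion applies when "The time interval from injury to randomisation exceeds 72 hours". The one exclusion on anticoagulant use is "Current use of anticoagulation for an alternative indication, with a clinical decision to continue". The paragraph beneath the list deals with anticoagulation that predates the injury: "If there is a clinical indication to continue the anticoagulation for a reason other than for VTE prophylaxis, the patient will be excluded". Neither statement mentions PTP begun since the injury.

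**Care before randomisation (9.3.3, 11.2).** Whether and when to start PTP is left to the clinical team in current practice. Consent may have to wait for a legal representative's visit.

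**Late arm (9.3.2, 9.3.4).** Section 9.3.4 gives the arm as "defined as administration of PTP after a minimum of 120 hours from TBI or PTP not administered at clinical discretion" and adds that "PTP should not be administered within 120 hours and administration will be recorded as protocol deviation". Section 9.3.2 puts the instruction at allocation, "Upon randomisation, patients will have PTP omitted", and also says that none is offered during the first 120 hours counted from injury. Neither section says how a dose given before allocation is to be treated.

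**Analysis (15.1).** The principal analysis is by intention to treat in all randomised patients.

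**The concern.** The late arm's clock starts at injury, but allocation can come as late as 72 hours after it. In between, the patient is in routine care, where PTP may be started. If it has been, the patient is still eligible as the criteria are written, and the two arms are affected differently. Allocated early, the patient already satisfies the arm's definition. Allocated late, the patient already fails it, and nothing done after randomisation can change that.

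For these patients the trial compares continuing PTP with interrupting it, not starting early with starting late. Randomisation still balances them between the arms, so there is no confounding. But they narrow the contrast that the trial was designed to measure, and an analysis of all randomised patients keeps them in. Sites also have no common rule: one may regard such a patient as unsuitable, another may enrol the patient and record a deviation, and a third may enrol and record nothing.

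**Working it through.** **1. Can it happen under the text?**

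| Question | Where | Answer |
|---|---|---|
| Latest randomisation | 9.2 | 72 h from injury |
| May PTP be started before then? | 9.3.3 | Yes, at clinical discretion |
| Does a criterion exclude it? | 9.1, 9.2 | No. The anticoagulant exclusion is for another indication, and the explanatory paragraph is limited to reasons other than VTE prophylaxis |
| Do the two equipoise exclusions catch it? | 9.2 | No. They concern active bleeding, and haemorrhage progression or neurological instability |
| Start of the late arm's 120 h | 9.3.2, 9.3.4 | Injury |

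The route is open.

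**2. How often?** The protocol gives no figure for PTP before randomisation. Section 6.3 reports, from the retrospective cohort, that "there was much heterogeneity in the timing of initiating PTP among different centres", and that patients with major extracranial injury were more likely to receive PTP. Section 9.3.2 gives a median of 5 days from injury to PTP and says that 50% receive none in routine care. If the median is among treated patients (an assumption; the text does not say), about 0.5 × 0.5 = 25% of all patients have started by 120 h. Fewer would have started by 72 h, and fewer again before randomisation, because 9.3.3 has patients screened promptly after admission. A low share is plausible but is not established.

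**3. The plan's own sample size (15.3).** Two-proportion formula with pooled variance under the null, two-sided 5%, 90% power, 1:1 allocation (sidedness and ratio are not stated; these values are assumed), no continuity correction:

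- 10% vs 5%: 1164 (stated 1164)
- 12% vs 7%: 1442 (stated 1441)
- 10% vs 5.4%: 1408 (stated 1441, within 3%)

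Evaluable after 5% loss: 1512 × 0.95 = 1436, or 718 per arm.

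**4. Dilution.** Let f be the share of the late arm dosed before randomisation and k the share of the early-arm benefit that those patients retain. Both are assumptions. The late-arm risk becomes

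p_L′ = p_L − f·k·(p_L − p_E)

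and, with d = p_L′ − p_E and p̄ the mean of the two risks,

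power = Φ[(d − 1.96·√(2p̄(1−p̄)/n)) / √((p_L′(1−p_L′) + p_E(1−p_E))/n)], n = 718.

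Example, 10% vs 5%, f = 5%, k = 1: p_L′ = 0.10 − 0.05 × 0.05 = 0.0975, d = 0.0475, p̄ = 0.07375. The null standard error is 0.01379 and the alternative 0.01374, so (0.0475 − 1.96 × 0.01379)/0.01374 = 1.49 and power = 93.2%.

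| Scenario | k | f = 0 | 2% | 5% | 10% |
|---|---|---|---|---|---|
| 10% vs 5% | 1 (upper bound) | 95.0% | 94.3% | 93.2% | 90.9% |
| 10% vs 5% | 0.5 | 95.0% | 94.7% | 94.1% | 93.2% |
| 12% vs 7% | 1 (upper bound) | 89.9% | 88.8% | 87.1% | 83.8% |
| 12% vs 7% | 0.5 | 89.9% | 89.4% | 88.6% | 87.1% |

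With k = 1 the expected difference of 5 points shrinks by f × 5 points: 0.1, 0.25 and 0.5 points at 2%, 5% and 10%.

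**The case against.** The strongest reply is that this will be rare and its effect small. The median of 5 days, the half who receive nothing and the clinician reluctance described in 6.1 and 6.2 all point that way. The increase from 1164 to 1441 evaluable patients also gives the base case a reserve: 10% vs 5% stays above 90% power with 10% of the late arm affected, even at full early-arm risk. That stands. It does not cover 12% vs 7%, one of the two scenarios used to support 1441, which has no reserve. Nor does a low average rule out clustering at early-starting sites or among patients with extracranial injury, which is both a stratification factor and a planned subgroup factor.

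A second reply is that a pragmatic trial should take patients as they come, and that inpatient records, which 10.3.2 uses for compliance, would show the earlier dose. This is a fair reason to prefer recording over exclusion. It does not settle how the dose is classified.

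A reader might infer three stronger things that the documents do not support:

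- **That such patients have in effect received early PTP.** Under 9.3.2 PTP is omitted from randomisation in the late arm, whereas under 9.3.1 it continues in the early arm until a clinical decision to stop. A dose or two followed by omission need not carry the full benefit, so k = 1 is a bound and not an estimate.
- **That each is a protocol deviation at entry, inflating the deviation count.** The sentence in 9.3.4 can be read that way, but 9.3.2 frames omission as acting from randomisation. The text is ambiguous.
- **That both the survey and the cohort show varied start times.** Section 6.3 credits this to the cohort alone. The survey findings listed there concern the state of the evidence and the factors behind decisions.

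**Conclusion.** The gap holds and is minor. Followed as written, the protocol allows a patient dosed since injury to be randomised to an arm defined by not having been dosed, and it does not say what follows. The effect is asymmetric and pulls the intention-to-treat difference towards zero.

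Its size depends on two quantities that the protocol does not give: the share affected and the benefit that those patients retain. With 2% to 5% affected and full early-arm risk, the loss is about 1 to 3 points of power; at 10% it is about 4 points for 10% vs 5% and 6 for 12% vs 7%. With half the benefit retained, the losses are roughly half of these. A serious loss of power cannot be inferred: it would need a share well above what the cohort figures in 9.3.2 suggest. The case for acting is that the classification should be fixed before enrolment. Prior PTP is a baseline fact, so a rule on it brings no post-randomisation selection, whereas removing such patients at analysis would depart from the stated population.

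**What to change.** Reconcile 9.2 with 9.3.2 and 9.3.4. The direct way is one line in 9.2 making it a condition of eligibility that no PTP dose has been given between the injury and randomisation, with this reason entered on the screening log that 11.3.2 already requires. The cost is one eligibility line and a slightly smaller eligible pool, mainly at sites that start early. The log would also show how common prior dosing is, which could be reviewed during the internal pilot.

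If the sponsor prefers to keep these patients for pragmatic reasons, add the prior dose and its time to the baseline items in 11.4, and state in 9.3.4 whether a dose given before randomisation counts as a late-arm deviation. This leaves the population unchanged and accepts the small dilution knowingly. Either choice closes the gap. Neither alters how PTP is given or withheld in clinical care.

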9.3 Treatment assignment

Patients who fulfil the eligibility criteria will be randomly assigned to the early pharmacological thromboprophylaxis (PTP) administration arm (<72 hours) or the late PTP administration arm (prescription of PTP deferred by a minimum of 120 hours or PTP not prescribed if deemed unnecessary by the clinical team).

Masking

It will not be possible to mask the intervention as we consider it unsafe, impractical, and costly. For example, if there is progression of an intracranial haemorrhage it is important for the clinical team managing the patient to understand the timing and number of doses administered of PTP for patient safety and to guide decision making on use of reversal agents. Our design includes blinded assessment of several secondary outcomes (e.g. GOS-E) to minimise bias from knowledge of treatment assignment.

9.3.1 Early PTP administration trial arm

Upon randomisation, patients will be administered a PTP agent within 72 hours of injury. The agent will continue to be administered until a clinical decision to stop. The VTE prophylaxis agent used route of administration and dose will be as per local hospital practice. The treating team will be encouraged to follow NICE guidance regarding the type and initiation of mechanical VTE prophylaxis.

Following multi-stakeholder discussions, including patient representatives, we decided the definition of early PTP administration as being at any time point up to 72 hours from TBI. This cut-off is also supported by the existing literature and by the findings of our survey. There is also mechanistic evidence to support this threshold for initiation - previous work highlights a 24-48h time point as the transition period for trauma-induced coagulopathy from a hypo-coagulable state to a hyper-coagulable one (32,33). Our group of clinical stakeholders agreed that this time period allows the necessary time to consider other injuries and interventions, facilitate interval brain imaging as necessary and provide the necessary assurance on clinical trajectory.

9.3.2 Late PTP administration trial arm

Upon randomisation, patients will have PTP omitted. However, if deemed necessary by the clinical team, PTP prophylaxis can be administered 120 hours after injury. This will be continued until a clinical decision to stop. The VTE prophylaxis agent used route of administration and dose will be as per local hospital practice. The treating team will be encouraged to follow NICE guidance regarding the type and initiation of mechanical VTE prophylaxis.

We discussed the definition of late PTP at length with our multi-stakeholder group and patient representatives considering the feedback received at the stage 1 application. Our clinical stakeholders had significant reservations about being asked to defer PTP for >7 days in keeping with the currently running Canadian randomised trial (34). Our service evaluation data supports the proposal of deferring PTP in the late arm by a minimum of 5 days (120h), as the median time to PTP from TBI was 5 days in this population and in a recent prospective study in critically ill trauma patients the median time to VTE was 6 days (35). However, our advisory group highlighted the potential bias that may occur with mandated prophylaxis at 5 days, when our service evaluation suggests that 50% of this population currently receive no prophylaxis at all within routine care. As such, in the late arm, PTP will not be offered for the first 120 hours after injury; after 120 hours, PTP can be prescribed if deemed necessary by the clinical team. We believe these decisions are also supported by the existing literature as referenced above and offer the maximum opportunity for pragmatic recruitment, separation of

interventions and evaluation of the specific research question as to whether early initiation is better than managed consideration of risk in current practice.

9.3.3. Difference between current & planned care pathways

There is no standardised NHS pathway for PTP following TBI. The decision to start PTP and the timing of such is left to the clinical team's discretion (5, 12). The NICE guidance (Venous thromboembolism in over 16s: reducing the risk of hospital-acquired deep vein thrombosis or pulmonary embolism NICE guideline [NG89]) states that PTP should be offered to people with serious or major trauma as soon as possible after the risk assessment when the risk of VTE outweighs the risk of bleeding but also that PTP should not be offered to patients with traumatic intracranial haemorrhage until the patient's condition has stabilised. These recommendations are entirely open to clinician interpretation and discretion, resulting in significant variation in practice even for patients with similar characteristics.

The allocated initiation and timing of VTE prophylaxis is the only difference in the planned care pathway for this study with all other aspects of clinical care following standard pathways.

Patients will be screened for eligibility promptly after admission, and written consent (or delegated consent by next of kin (personal legal representative) or professional consultee (Independent healthcare professional) will be sought prior to enrolment and randomisation. This tiered consent approach has been successfully used in recent TBI trials (36, 37). Patients deteriorating neurologically will usually have a repeat CT brain imaging with further management as required. Patients developing symptoms of a VTE will be managed as per normal clinical pathways. These usually include Doppler ultrasound if a deep vein thrombosis is suspected or a CTPA if a pulmonary embolism is suspected, with treatment dose anticoagulation for three months initiated as required, or siting of an inferior vena cava filter if the treating team consider therapeutic anticoagulation to be absolutely contraindicated. Clinical follow-up for the TBI is usually 3-6 months after discharge. If a VTE has been diagnosed, this can either be managed by the patient's GP, or it may be necessary to follow up in a thrombosis clinic, respiratory clinic and/or referral to a cardiac-pulmonary rehabilitation programme for those who have suffered a significant, symptomatic VTE.

9.3.4. Randomisation

A secure web-based randomisation service (Sealed Envelope) will be used for the randomisation of eligible patients. Suitably trained staff will access the secure website and enter the necessary information. The system will provide an immediate allocation along with the patient identifier number for the trial. A confirmatory email will be sent to the email addresses of the study team members at the site randomising the patient. Trial investigators (or delegates) from the central team will be available 24-hours in case of problems or queries with the randomisation system. The presence of extracranial injury and initial admission to the ward vs critical care will stratify allocation. Stratified block randomisation will be used.

Early PTP arm - defined as administration of PTP within 72 hours of TBI

Late PTP arm - defined as administration of PTP after a minimum of 120 hours from TBI or PTP not administered at clinical discretion. PTP should not be administered within 120 hours and administration will be recorded as protocol deviation

9.4 Participant withdrawal criteria

Primary reasons for withdrawal may include:

- Suspected Unexpected Serious Adverse Reaction (SUSAR)
- Withdrawal from treatment - participants may voluntarily withdraw from treatment for any reason at any time but continue to provide follow-up data (via patient completed questionnaires and/or NHS England data or the Scottish, Welsh or Northern Irish equivalents, where applicable)
- Withdrawal from trial - participants may voluntarily withdraw from treatment for any reason at any time and withdraw from data collection
- Participants will be withdrawn at any time if the investigator concludes that it would be in the participant's best interest for any reason

Each participant has the right to discontinue their participation in the trial at any time. If an unconscious participant regains capacity and makes a request to be withdrawn from the trial, then this will be accepted. Incapacitated participants may withdraw from the trial if the consultee requests withdrawal.

As the trial is on an intention-to-treat basis, any data collected will remain in the trial, and the participant will continue to be followed up unless consent to continue data collection has been withdrawn. Initially, participants who have been withdrawn from the trial will not be replaced as the power calculation for the trial allows for a 5% loss to follow-up; however, the withdrawal rate will be monitored, and participant replacement will be at the discretion of the Trial Steering Committee should it exceed 5%.

All discontinuations and withdrawals will be documented in the CRF. If a participant wishes to discontinue, anonymised data collected up until that point will be included in the analysis.

10. Trial treatments

10.1 Treatment summary

The IMPs in this trial are VTE prophylaxis agents used in standard clinical practice (listed in **Table 1**). This trial has been accepted as Type A against the competent authority risk-adaptation criteria, i.e. 'no higher than the risk of standard medical care'

All prescribing, storage, administration and dosing decisions will be taken in line with local Trust guidelines and the published summary of product characteristics (SmPC) for each PTP agent.

